10.1 Actinic Keratoses Lesion Counts

AK lesions will be counted at Baseline, Day 60/EOT, and Day 90/EOS. At the Baseline Visit (Visit 1), all AK lesions in the 25 cm² treatment area, independent of size, will be identified, counted, and recorded on the transparency. The number and location of AK lesions to be treated that are ≥ 4 mm in diameter and the diameter of each AK lesion in the 25 cm² treatment area will also be documented at the Baseline Visit. The suggested procedure for AK counting and definition of face (excluding ears) and bald scalp will be detailed in a separate document. At the Baseline Visit, the 25 cm² treatment area must include at least five and no more than 10 clinically typical, visible, or palpable, discrete, nonhyperkeratotic, nonhypertrophic, AK lesions, each at least 4 mm in diameter, contained within a continuous 25 cm² treatment area located on the face (excluding ears) or bald scalp. At the EOT and EOS visits, the number of total AK lesions in the 25 cm² treatment area will be counted and the number of new AKs will be identified. A new AK is defined as a lesion that was not present at the Baseline Visit.

NOTE: To ensure accurate identification of the treatment area, the site must use the transparency and the Baseline photo as necessary to locate the selected treatment area.

If the subject has a LSR that prevents the investigator or designee from performing the AK count at a visit, the investigator or designee should document in the source document and CRF that the AK count was unable to be obtained due to a LSR.

10.2 Local Skin Reaction Assessment

At Baseline, Day 30 follow-up, Day 60/EOT, Day 90/EOS, and Unscheduled Visits (if applicable), the investigator or designee will assess the 25 cm² treatment area and rate on a scale of 0 = absent, 1 = mild (slight, barely perceptible), 2 = moderate (distinct presence), and 3 = severe (marked, intense) the following LSRs:

- Erythema
- Dryness/flaking/scaling
- Burning/stinging
- Erosion/ulceration
- Edema
- Pain (within the last 24 hours)
- Pruritus (itching) (within the last 24 hours)

These LSRs will be collected independently of AEs. Any LSR that occurs **within the 25 cm² treatment area (face [excluding the ears] or bald scalp) and extends to adjacent surrounding skin (defined to be up to a 5 cm border around the 25 cm² treatment area)** will be considered LSRs. LSRs that require medical intervention

(prescription medication) or extend beyond the 5 cm surrounding skin should be documented as an AE.

11. PHOTOGRAPHY

Photography documentation is required in this study. Photographs taken as part of this study will be used to document proper identification of the treatment area to help ensure proper application of the test article by the subject. Photographs may also be used to document the effects of treatment, AEs, or other findings during the study. The site will be provided with suggested guidelines to assist them in taking standardized photographs. All photographs taken as part of this study are for informational purposes only and are not to assist in grading or for any other assessment.

Note: Subjects who decline to have Baseline photographs taken will not be eligible to be in the study. Additional details regarding taking Baseline photographs are provided in a separate photo guide (i.e., the Treatment Area Identification Manual) provided to the site.

12. LABORATORY TESTS

12.1 Urine Pregnancy Tests

UPTs must be performed on all WOCBP at Baseline prior to randomization and at the Day 60/EOT visit. All WOCBP must have a negative UPT at Baseline to be eligible for study entry. The UPTs will be performed at the study site, if the site is registered and conforms to CLIA regulations for such testing (possesses a current valid CLIA Certificate of Waiver), or at an appropriately registered reference laboratory. The investigator will report the UPT results on the CRFs, in the subject's medical records, and in independent records maintained at the study site. The UPT used must have a minimum sensitivity of 25 mIU of β -hCG/mL.

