5.1.3 Subject Withdrawal Criteria

Procedures for handling subjects who are discontinued from the study are described in [Section 13.2](#). Subjects who are discontinued will not be replaced.

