6.3.4 Other Considerations

These test articles are for topical use only (not for oral, ophthalmic, or intravaginal use). Contact with eyes, lips, and nostrils should be avoided. If contact with the mouth or eyes occurs, rinse thoroughly with water right away.

Areas treated with the test article should not be covered with any type of bandage or occlusive dressings.

Subjects with a known sensitivity to any of the ingredients in the test articles should not participate in this study.

In case of accidental ingestion, subjects should contact the investigator immediately.

The effects of the test article in nursing mothers, pregnant women and their unborn children are unknown. WOCBP must not be pregnant or planning a pregnancy during the study period.

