9.3 Visit 3 (Day 30 \pm 3 days): Follow-Up

At this visit, the investigator or designee will:

- Query the subject about any changes in health status or any AEs since the last visit. Document in the AE section of the CRF, as appropriate.

- Record any changes in the subject's concomitant medications and therapies/procedures.
- Use the transparency and the Baseline photo as necessary to locate the selected treatment area.
- Perform the LSR assessment as described in [Section 10.2](#).
- Review/collect/distribute the subject diary as necessary.
- Review test article compliance. Test article application will be demonstrated if deemed necessary. As necessary, the Baseline photograph and the template may be used as a visual aid to re-instruct subject on proper application of the test article to the treatment area.
- The subject's tube of test article will be weighed and re-dispensed.
- Remind the subject to continue to apply test article twice daily, once in the morning and once in the evening, to the skin of the 25 cm² treatment area until the next clinic visit.
- Confirm the next appointment.

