9.6 Visit 6 (Day 90 \pm 4 days): End of Study

At this visit, the investigator or designee will:

- Query the subject about any changes in health status or any AEs since the last visit. Document in the AE section of the CRF, as appropriate.
- Record any changes in the subject's concomitant medications and therapies/procedures.
- Use the transparency and the Baseline photo as necessary to locate the selected treatment area.
- Perform the AK lesion count as described in [Section 10.1](#), which includes any AKs ≥ 4 mm in diameter, as well as any smaller lesions.
- Perform the LSR assessment as described in [Section 10.2](#).
- Discharge the subject from the study.

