9.7 Unscheduled Visit

The investigator may see the subject at an unscheduled visit to manage any AEs or LSRs.

At this visit, the investigator or designee will:

- Query the subject about any changes in health status or any AEs since the last visit. Document in the AE section of the CRF, as appropriate.
- Use the transparency and the Baseline photo as necessary to locate the selected treatment area.
- Perform the LSR assessment as described in [Section 10.2](#).
- Record any changes in the subject's concomitant medications.
- Review subject diary and the requirements for test article application, if applicable.
- Confirm the next appointment.

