13.2 Subject Discontinuation

A subject may be withdrawn from the study prior to completion for any of the following reasons:

- AEs
- Death

- Lack of efficacy
- Lost to follow-up
- Noncompliance with study drug
- Physician decision
- Pregnancy (if applicable)
- Progressive disease
- Protocol deviation
- Study terminated by Sponsor
- Withdrawal by subject; NOTE: if the subject decides to withdraw from the study due to an AE then it should be classified as withdrawal due to an AE.
- Other (e.g., any reason that may affect the outcome of the study or safety of subjects)

If a subject withdraws prematurely for any reason, the site should make every effort to have the subject return for; a) their next scheduled visit to perform all required visit activities and to collect and reconcile all test article AND b) return for the EOS visit (Day 90) to perform all required visit activities and complete the EOS CRF. If the subject will not agree to return for the EOS visit, the site should complete the EOS CRFs during the last visit that the subject will complete. Subjects who withdraw prematurely will not be replaced. When a subject is withdrawn from the study for a treatment-related AE (i.e., as defined in [Section 14](#)), when possible, the subject should be followed until resolution or stabilization of the AE. If a subject is discontinued from the study due to pregnancy, the pregnancy and its outcome should be followed (see [Section 14.5](#)).

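### A woman of childbearing potential withdrawn before Visit 3 has no scheduled pregnancy test after exposure, and early-termination skin reaction scores can enter the SAP's Day 90/EOS row

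*Protocol*

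**What the plan says.** **When the test is done.** Protocol 12.1: "UPTs must be performed on all WOCBP at Baseline prior to randomization and at the Day 60/EOT visit". The schedules in both documents mark the test at Visits 1 and 5 only. Visit 5 (Protocol 9.5) is the only post-baseline visit whose activity list names it.

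**What happens on early withdrawal.** Protocol 5.1.3: "Procedures for handling subjects who are discontinued from the study are described in" Section 13.2. That section sets two steps for the site to pursue: "return for; a) their next scheduled visit to perform all required visit activities and to collect and reconcile all test article AND b) return". The second step is the Day 90 visit. If the subject refuses Day 90, "the site should complete the EOS CRFs during the last visit that the subject will complete".

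**What the other visits contain.** Visit 3 (9.3) covers adverse events, medications, skin reactions, compliance, tube weight and the diary ("Review/collect/distribute the subject diary as necessary"). Visit 6 (9.6) covers adverse events, medications, the lesion count and skin reactions, and ends with "Discharge the subject from the study". Section 9.7 adds an optional visit: "The investigator may see the subject at an unscheduled visit to manage any AEs or LSRs". None of the three lists contains a pregnancy test.

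**What the SAP says.** SAP 7.2.4 places the second test at Day 60/EOS, not Day 60/EOT. SAP 6 defines EOT as Visit 5/Day 60, and EOS as either Visit 6/Day 90 or an early-termination visit. SAP 8.8.2 tabulates skin reactions at Baseline, Day 30, Day 60 and Day 90/EOS. Protocol 17.3.2.3 asks for tabulation by onsite clinic visit.

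**The concern.** The pregnancy test is tied to one post-baseline visit, and the early-withdrawal procedure does not always pass through that visit. A woman exposed to gel for some weeks and then withdrawn can therefore do everything asked of her and never have a scheduled test, while every woman who reaches Day 60 has one.

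The protocol's own safety provisions give this its weight. Section 6.3.4 states: "The effects of the test article in nursing mothers, pregnant women and their unborn children are unknown". Section 14.5 requires immediate notification of a pregnancy exposed to test article, and follow-up of offspring for at least eight weeks. Those duties begin only once a pregnancy has been found.

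The skin reaction issue comes from the same early-termination route. Day 90 is meant to show the skin about 30 days after treatment ends. A score taken while gel is in use or just after it stops describes something else, and pain and pruritus are rated over the preceding 24 hours (Protocol 10.2), so timing matters. Mixing the two can make reactions look more persistent than they are, more so in an arm with more withdrawals for poor tolerability.

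**Working it through.** There is no planned figure to reproduce. The check traces each route through Section 13.2 against the visit lists, counting scheduled pregnancy tests after first exposure.

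| Situation of a WOCBP | Next scheduled visit | Then | Scheduled tests |
|---|---|---|---|
| Withdrawn before Visit 3, returns at Day 90 | Visit 3 (or the Visit 2 call): none | Visit 6: none | 0 |
| Withdrawn before Visit 3, refuses Day 90 | Last visit attended, EOS forms completed: none | – | 0 |
| Withdrawn between Visits 3 and 4, only clinic visits count | Visit 5: test | Visit 6: none | 1 |
| Withdrawn between Visits 3 and 4, the phone call counts | Visit 4 call: none | Visit 6: none | 0 |
| Withdrawn after Visit 4, before Visit 5 | Visit 5: test | Visit 6: none | 1 |
| Stops gel but stays in the study | Visit 5 as planned: test | Visit 6: none | 1 |

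The first two rows give zero on any reading. The early-termination footnote to the schedule adds only Day 90 activities, which include no test. The rows for withdrawal between Visits 3 and 4 depend on whether a phone contact is a visit. The protocol numbers the calls as Visits 2 and 4. But 13.2 speaks of returning and handing back gel, which fits a clinic visit better. The text does not settle it.

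**SAP 7.2.4.** Read literally with the SAP 6 definition of EOS, its label could reach an early-termination visit. However, the SAP's own schedule (SAP 5) marks the test at Visits 1 and 5 only, and Protocol 12.1 says Day 60/EOT. The label looks like a slip, and sites work from the protocol.

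**Skin reactions.**
1. SAP 6: an early-termination visit is an EOS visit.
2. SAP 8.8.2: the last tabulated time point is Day 90/EOS, with no separate early-termination category.
3. Together, an early-termination score qualifies for that row whatever the study day.
4. A subject who follows 13.2 in full also has a true Day 90 score, and the SAP does not say which one is tabulated. A subject who refuses Day 90 has only the early score, so mixing arises mainly there.

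For scale, about 600 subjects randomized 1:1:1 give 600/3 = 200 per arm, so one score is about 1/200 = 0.5 percentage points of a fully attended row. The documents do not say how many such scores to expect.

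**The case against.** The strongest reply is that other safeguards cover these women. Effective contraception is required. Section 14.5 tells WOCBP to contact the investigator at once if they suspect pregnancy, for example after a missed or late period, and provides for laboratory testing on suspicion at any time in the study. Visits 3 and 6 both ask about changes in health. A woman withdrawn before Visit 3 who returns at Day 90 is asked again nominally at least 90 − 30 = 60 days later, when a pregnancy begun during exposure would usually have shown itself. This stands, and it is why the gap is small. It does not close the gap, because the protocol did not rely on suspicion alone for women who reach Day 60.

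A reader might infer that any woman who stops the gel before Visit 3 goes untested. The documents do not support that. Section 13.2 applies to withdrawal from the study, and a woman who stops applying gel but stays in still attends Visit 5, where all WOCBP are tested. Nor can it be said that withdrawn women can get no test at all; what is missing is a scheduled one.

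On skin reactions, it is fair to say that SAP 8.8.2 does not state that early scores enter the row; that follows only from joining it to SAP 6. Day 90/EOS also appears elsewhere as a plain visit label (Protocol 10.2, SAP 7.1.1 and 7.2.2). The tables are descriptive, carry no test, and are backed by a subject listing (16.2.7.3). This narrows the point to an ambiguity worth removing.

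**Conclusion.** The concern holds in a limited form and is minor. A WOCBP withdrawn from the study before Visit 3 who follows Section 13.2 exactly has zero scheduled pregnancy tests after exposure. Withdrawals between Visits 3 and 4 join her if the Visit 4 call counts as the next scheduled visit. SAP 7.2.4 is inconsistent with Protocol 12.1 and SAP 5 and does not repair this.

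SAP 6 and 8.8.2 read together also allow early-termination skin scores, mainly from subjects who do not return at Day 90, into the Day 90/EOS row.

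The size is unknown: the documents give neither the number of early withdrawals nor the number of WOCBP, and that number may be very small. A reader might infer that the mixed row could disturb the equivalence or superiority conclusions. It cannot: those rest on lesion clearance, and the skin reaction table feeds no test.

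**What to change.** 1. In Protocol 12.1, 13.2 and the pregnancy test row of the schedule (with its copy in SAP 5), keep the Day 60/EOT test for every WOCBP still in the study and add: *WOCBP withdrawn from the study before Visit 5 have a UPT at the last clinic visit they attend (Day 90 if they return, otherwise the early-termination visit).* The rule should be tied to withdrawal, not to stopping gel. Otherwise it would replace the Day 60 test for women who stay in, possibly with one too soon after the last dose to detect a recent conception. Day 90 is preferred for the same reason.
2. Correct SAP 7.2.4 to Day 60/EOT, or at early withdrawal.
3. In SAP 8.8.2, let the Day 90 row take Visit 6 scores only, and show early-termination scores in a separate row. Leave SAP 6 and 8.2.2 as they are, so that mITT membership does not move.

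**Cost.** A sentence or two of text, one urine test for a few early withdrawals, and one extra row in the skin reaction tables. Test kits are already supplied (Protocol 16.2) and 13.2 already asks for the visits. A woman who agrees to return at Day 90 and then does not would still be missed; a site that doubts her return can test at the earlier visit as well.

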13. END OF STUDY CRITERIA

At the end of each subject's participation in the study, the investigator will complete an End of Study form for all completed and discontinued subjects.

13.1 Completion of the Study

Subjects who complete the 60-day treatment and all of the EOS visit evaluations at Day 90 will be considered to have completed the study.

13.2 Subject Discontinuation

A subject may be withdrawn from the study prior to completion for any of the following reasons:

- AEs
- Death

- Lack of efficacy
- Lost to follow-up
- Noncompliance with study drug
- Physician decision
- Pregnancy (if applicable)
- Progressive disease
- Protocol deviation
- Study terminated by Sponsor
- Withdrawal by subject; NOTE: if the subject decides to withdraw from the study due to an AE then it should be classified as withdrawal due to an AE.
- Other (e.g., any reason that may affect the outcome of the study or safety of subjects)

If a subject withdraws prematurely for any reason, the site should make every effort to have the subject return for; a) their next scheduled visit to perform all required visit activities and to collect and reconcile all test article AND b) return for the EOS visit (Day 90) to perform all required visit activities and complete the EOS CRF. If the subject will not agree to return for the EOS visit, the site should complete the EOS CRFs during the last visit that the subject will complete. Subjects who withdraw prematurely will not be replaced. When a subject is withdrawn from the study for a treatment-related AE (i.e., as defined in [Section 14](#)), when possible, the subject should be followed until resolution or stabilization of the AE. If a subject is discontinued from the study due to pregnancy, the pregnancy and its outcome should be followed (see [Section 14.5](#)).

13.3 Study Termination

The study may be terminated by the investigator or the Sponsor. If, in the opinion of the investigator, clinical observations made during the study suggest that it may be unwise to continue, he or she may stop the study. A study termination by the investigator will be reported to the Sponsor.

In addition, a written statement fully documenting the reasons for this action will be submitted to the Sponsor by the investigator within five working days.

In the event that the Sponsor chooses to discontinue or terminate the study, appropriate notification will be given to the investigator.

14. ADVERSE EVENT REPORTING

14.1 Adverse Event Definitions

An **adverse event** is any untoward medical occurrence associated with the use of a drug in humans, whether or not considered drug related.

An AE (also referred to as an adverse experience) can be any unfavorable and unintended sign (e.g., an abnormal laboratory finding), symptom, or disease temporally associated with the use of a drug, and does not imply any judgment about causality. An AE can arise with any use of the drug (e.g., off-label use, use in combination with any drug) and with any route of administration, formulation, or dose, including an overdose.

Suspected adverse reaction is any AE for which there is a reasonable possibility that the drug caused the AE. "Reasonable possibility" means there is evidence to suggest a causal relationship between the drug and the AE. A suspected adverse reaction implies a lesser degree of certainty about causality than adverse reaction, which means any AE caused by a drug.

An **adverse reaction** is any AE caused by a drug. Adverse reactions are a subset of all suspected adverse reactions for which there is reason to conclude that the drug caused the event. For the purposes of prescription drug labeling, the term adverse reaction is defined to mean "an undesirable effect, reasonably associated with the use of a drug that may occur as part of the pharmacological action or may be unpredictable in its occurrence. This definition does not include all AEs observed during use of a drug, only those AEs for which there is some basis to believe there is a causal relationship between the drug and the occurrence of the AE".

An AE or suspected adverse reaction is considered "unexpected" if it is not listed in the RLD package insert or is not listed at the specificity or severity that has been observed. For example, under this definition, hepatic necrosis would be unexpected (by virtue of greater severity) if the RLD package insert referred only to elevated hepatic enzymes or hepatitis. Similarly, cerebral thromboembolism and cerebral vasculitis would be unexpected (by virtue of greater specificity) if the RLD package insert listed only cerebral vascular accidents. "Unexpected," as used in this definition, also refers to AEs or suspected adverse reactions that are mentioned in the RLD package insert as occurring with a class of drugs or as anticipated from the pharmacological properties of the drug, but are not specifically mentioned as occurring with the particular drug under investigation.

Timely and complete reporting of all AEs assists [REDACTED] in identifying any untoward medical occurrence, thereby allowing:

- 1) protection of the safety of study subjects;
- 2) a greater understanding of the overall safety profile of the test article;
- 3) recognition of dose-related test article toxicity;
- 4) appropriate modification of study protocols;
- 5) improvements in study design or procedures; and
- 6) adherence to worldwide regulatory requirements.

14.2 Adverse Event Details

AEs may be either spontaneously reported or elicited during questioning and examination of a subject. All AEs must be recorded on the AE CRF. If known, the investigator should report the diagnosis of the underlying illness or disorder, rather than its individual symptoms. Subjects experiencing AEs that cause interruption or discontinuation of test article or those experiencing AEs that are present at the end of their participation in the study should receive follow-up as appropriate. AEs should be followed to resolution or stabilization (if possible) and, if they become serious, reported as serious adverse events (SAEs, see [Section 14.3](#)). If possible, the outcome of any AEs that caused permanent discontinuation or that were present at the end of the study, especially those considered by the investigator to be related to the test article, should be reported.

Information on the medical condition of subjects should begin following the subject's written consent to participate in the study and a medical history should be taken at screening. During any wash out and baseline periods, any changes in the health of subjects should be recorded as changes in medical history unless an event occurred as a result of a study-related procedure and is unanticipated; in such cases, the event should be recorded as an AE and reported to the Institutional Review Board (IRB) as an "unanticipated problem" in accordance with local procedures. Other changes in subject health information becomes AE data when the subject begins dosing with the test article; therefore, AE data should be collected from the date of the first dose of test article until the date of the final study visit. These data are considered treatment-emergent AEs.

The investigator will instruct the subject to report any AEs that may occur during the study. At each visit, the investigator should ask the subject, in non-directive fashion, about any change in the subject's overall health status since the previous visit.

The severity of each AE, as judged by the investigator, will be recorded on the appropriate AE CRF and will be graded according to the following scale:

Mild - The AE is usually transient and may require only minimal treatment or therapeutic intervention. The event does not generally interfere with usual activities of daily living.

Moderate - The AE is usually alleviated with additional specific therapeutic intervention. The event interferes with usual activities of daily living, causing discomfort, but poses no significant or permanent risk of harm to the research participant.

Severe - The AE interrupts usual activities of daily living or significantly affects clinical status, or may require intensive therapeutic intervention.

The investigator must determine the relationship of the AE to the test article according to the following categories:

- Important medical events; a medical event(s) that may not result in death, be life-threatening, or require hospitalization but, based upon appropriate medical judgment, may jeopardize the subject and may require medical or surgical intervention to prevent one of the outcomes listed in the definition above. Examples of such medical events include allergic bronchospasm requiring intensive treatment in an emergency room or at home, blood dyscrasias or convulsions that do not result in inpatient hospitalization, or the development of drug dependency or drug abuse.

Events NOT considered to be serious AEs are:

- Hospitalizations for the treatment, which was elective or pre-planned, of a pre-existing condition that did not worsen, and
- Treatment on an emergency, outpatient basis, for an event not fulfilling any of the definitions of “serious” given above and not resulting in hospital admission.

AEs classified as “serious” by either the investigator or the Sponsor require expeditious handling and reporting to [REDACTED] to comply with regulatory requirements. **All SAEs, whether related or unrelated to test article, must be immediately reported by telephone to the Medical Monitor and, in the event that he/she is unavailable, to the Project Manager listed on the first page of the protocol.** Written notification of all SAEs should be sent to the Project Manager by email or confirmed facsimile transmission. These include those SAEs listed in the protocol or RLD Package Insert and must include an assessment of whether there is a reasonable possibility that the drug caused the event.

If only limited information is initially available, follow-up reports are required. Should the investigator become aware of a SAE (regardless of its relationship to test article) that occurs within 30 days after stopping the test article, the SAE must be reported in accordance with procedures specified in this protocol. In the event of death, if an autopsy is performed, a copy of the report should be sent to [REDACTED] if available.

Upon receiving such notices, the investigator must review and retain the notice with the RLD Package Insert and promptly submit a copy of this information to the responsible IRB according to local regulations. The investigator and IRB will determine if the informed consent requires revision. The investigator should also comply with the IRB procedures for reporting any other safety information. Where required, submission of safety updates by the investigator to Health Authorities should be handled according to local regulations.

The Sponsor or designee may be required to report certain SAEs to regulatory authorities (e.g., United States FDA) within seven calendar days of being notified about the event; therefore, it is important that investigators submit any information requested by the Sponsor or designee as soon as it becomes available.

